**CONFIDENTIAL**

204837

Reported Units	Multiplier
Units	1
Milliliters (ml or CC)	0.0025
Milligram (mg)	0.0025
Milligrams/millilitres (mg/ml)	0.0025

 
Where a non-integer number of units has been entered on the eCRF, this will be rounded up to the nearest integer prior to any subsequent derivation (if necessary).
 
	
Evaluation Period (Weeks 28 to 52)	

 
Only transfusion events with a start date from date of week 28 visit to the date of the week 52 visit will be included
 
Patient Years (PY) = (cumulative total time from date of week 28 visit to the date of the week 52 visit, for subjects who did not withdraw from study treatment during the evaluation period + cumulative time from date of week 28 visit to the date of withdrawal from study treatment, for subjects who withdrew from study treatment during the evaluation period) / 365.25
 
Transfusion Events per 100 PY = (100 * number of on-treatment RBC or whole blood transfusion events during the evaluation period) / Patient Years (PY)
 
Transfusions per 100 PY = (100 * number of on-treatment RBC or whole blood transfusions during the evaluation period) / Patient Years (PY)
 
Units per 100 PY = (100 * number of on-treatment RBC or whole blood transfusion units during the evaluation period) / Patient Years (PY)
 
	
Randomization to Week 52	

 
Only transfusion events with a start date from the date of randomization to the date of the week 52 visit will be included
 
Patient Years (PY) = (cumulative total time from date of randomization to the date of the week 52 visit, for subjects who did not withdraw from study treatment prior to week 52 + cumulative time from date of randomization to the date of withdrawal from study treatment, for subjects who withdrew from study treatment prior to week 52) / 365.25
 
Transfusion Events per 100 PY = (100 * number of on-treatment RBC or whole blood transfusion events from the date of randomization to the date of the week 52 visit) / Patient Years (PY)
 
Transfusions per 100 PY = (100 * number of on-treatment RBC or whole blood transfusions from the date of randomization to the date of the week 52 visit) / Patient Years (PY)
 
Units per 100 PY = (100 * number of on-treatment RBC or whole blood transfusion units from the date of randomization to the date of the week 52 visit) / Patient Years (PY)
 
	
Time to First On-Treatment RBC or Whole Blood Transfusion	

 
Event Date = Start date for the first on-treatment RBC or whole blood transfusion received after treatment start date
 
Censoring Date = date of stopping study treatment for subjects who stopped study treatment, or date of study completion for subjects who did not stop study treatment
 
Time to event (days) = date of event – treatment start date +1
 
Censored time (days) = censoring date – treatment start date + 1
 
	

CONFIDENTIAL

204837

 
• Person years (PY) = (cumulative total time to event date, for subjects who received at least one on-treatment RBC or whole blood transfusion + cumulative total of censoring time for subjects who did not receive at least one on-treatment RBC or whole blood transfusion) / 365.25
 
• Incidence rate per 100 PY = (100 * number of subjects who received at least one on-treatment RBC or whole blood transfusion) / person years
 
• Absolute rate difference (per 100 person years) = daprodustat incidence rate (per 100 person years) – rhEPO incidence rate (per 100 person years)
 


Time Period for On-Treatment Transfusions
 
The period for capturing on-treatment transfusions begins on the treatment start date. The end of this time period is defined as follows:
 
 
• For subjects whose treatment stop date is missing and who took study treatment, use date of study withdrawal/completion
 
• For subjects continuing on study past the treatment stop date, use (treatment stop date) For subjects whose study withdrawal/completion date is on or before (treatment stop date), use date of study withdrawal/completion
 

Model Specification
 
 
• Analysis of time to first RBC or whole blood transfusion will be performed using a Cox proportional hazards model adjusted for treatment and region.
 
• Analysis will include only transfusion occurring during the on-treatment period
 

Model Results Presentation
 
 
• The hazard ratio, two-sided 95% CI, and one-sided p-value for the superiority test will be presented for the comparison of daprodustat vs. rhEPO using the Cox Proportional Hazards model.
 
• Number and percentage of subjects who received at least one on-treatment RBC or whole blood transfusion and the number and percentage of censored subjects will be provided by treatment group. The incidence rate per 100 PY (95% CI) within each treatment group and the absolute rate difference per 100 PY (95% CI) will be displayed with the results of the Cox proportional hazards regression model. For within-group rates, the two-sided 95% CI will be obtained using an exact Poisson method. For difference in rates between treatments, the two-sided 95% CI will be constructed with a Normal approximation using Wald's method [Liu, 2006].
 
• A Kaplan-Meier plot will be produced showing the survival function for time to first RBC or whole blood transfusion.
 

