5. STUDY DESIGN

5.1. Overall Design

- This is a randomized, double-blind, active-controlled, parallel-group, multi-center study in hemodialysis-dependent participants, including combination methods such as hemodiafiltration or hemofiltration with HD, who have anemia of CKD and are currently treated with rhEPO or its analogs.
- This study includes a 4-week Screening Period, a 52-week Treatment Period and a Follow-up Period (Figure 1).
- The 52-week Treatment Period consists of:
 - The Stabilization Period (SP), defined as the period from Day 1 to Week 28 (up to but excluding the Week 28 visit), during which study treatment will be dose-titrated to achieve and maintain Hgb in the target range.
 - The Evaluation Period (EP), defined as the period from Week 28 to Week 52, to assess long-term efficacy and safety. The study treatment may be dose-titrated, if needed, during this period to achieve or maintain Hgb level in the target range.

Figure 1 Study Schematic

- Each participant will remain in the study for up to 62 weeks. Participants who permanently discontinue study treatment will remain in the study.

- Randomization will be stratified by region (see [Appendix 7](#)). Following stratification, participants will be randomized 2:1 to daprodustat or epoetin alfa. Daprodustat will be administered three-times weekly and epoetin alfa will be administered once weekly or three-times weekly, depending on dose level (Section 7).
- Due to the difference in formulations between the investigational product and active control (tablets versus IV injection), and in order to maintain the study blind, each participant will receive a tablet and an IV study treatment; one will be active and one will be inactive (Section 7). Participants randomized to receive daprodustat will also receive saline IV injection. Participants randomized to receive epoetin alfa will also receive placebo tablets.
- PK samples will be collected from all study participants to enable exposure-response and exposure-safety analyses (Section 9.5).
- Adjustment of both study treatments (tablet and IV injection formulations) will follow a protocol-specified study treatment dose adjustment algorithm to achieve and maintain Hgb within the target range of 10.0 to 11.0 g/dL, inclusive (Section 7.2). Dose changes will be made programmatically by the Interactive Response Technology (IRT) system for both study treatment arms.

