8.1.1. Procedures Following Discontinuation of Study Treatment

Participants who permanently discontinue study treatment will remain in the study. Participants will be asked to attend an Early Treatment Discontinuation visit and will be expected to attend study visits according to the SoA, [Table 2](#), unless consent is actively withdrawn.

- Early Treatment Discontinuation visit: This visit should occur within 2 weeks of stopping study treatment.
- Remaining in-clinic visits: Study visits at Weeks 4, 16, 28, 40 and 52. Phone visit is acceptable in exceptional circumstances.

If a participant does not agree to continue attending in-clinic or phone visits, other follow-up options to collect study outcomes and vital status for up to 52 weeks after the participant's randomization visit should be pursued according to local laws and regulations. If one of these alternate methods to collect study outcomes and vital status is acceptable to the participant, then the participant will be considered to have remained in the study and not to have withdrawn consent.

[figure not shown]

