### *RBC and Whole Blood Transfusions*

Endpoint / Variables

 
• Number (%) of participants who receive at least one RBC or whole blood transfusion by Week 52
 
• Number of RBC and whole blood transfusion events per 100 patient years
 
• Number of RBC and whole blood transfusions per 100 patient years
 
• Number of RBC and whole blood units per 100 patient years
 
• Time to first RBC and whole blood transfusion
 

Planned Exploratory Displays

 
• Summary and analysis tables will use the All Randomized (ITT) population.
 
• The total number of on-treatment RBC and whole blood transfusion events, transfusions and units for each subject will be derived as described in Section 14.6.3
 
• The number of on-treatment RBC and whole blood transfusion events per subject, the number of subjects with at least one RBC and whole blood transfusion event, and total number of RBC and whole blood transfusion events will be summarized.
 
• The number of on-treatment RBC and whole blood transfusion events per 100 patient years will be summarized by treatment group.
 
• The number of on-treatment RBC and whole blood transfusions per 100 patient years will be summarized by treatment group.
 
• The number of on-treatment RBC and whole blood units per 100 patient years will be summarized by treatment group.
 
• The reason for transfusion events will be summarized.
 
• The above summaries will be produced for the Evaluation Period and Week 52.
 
• An analysis of time to first RBC or whole blood transfusion will be performed as described in section 14.6.3, including a Kaplan-Meier plot.
 
• All transfusion summaries will be repeated for the primary definition of ESA hyporesponder subgroups (see Section 14.6.2).
 

CONFIDENTIAL

204837

*Dose Adjustment Scheme*

Endpoint / Variables

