#### 14.4.1.1. Study Phases for Hgb, Iron Parameters, IV Iron Dose Endpoints, Iron Use Summaries, Transfusion and PRO Data

Study Phase	Definition
Pre-Treatment	Date $\leq$ Study Treatment Start Date
On-Treatment	Study Treatment Start Date < Date $\leq$ Study Treatment Stop Date + 1 day
Post-Treatment	Date > Study Treatment Stop Date + 1 day
Post-Randomization	Randomization Date < Date

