**Standardized Monthly IV Iron Dose (mg/month) from Week 28 to Week 52 (EP Average Monthly IV Iron Dose)**

- In order to calculate the average monthly IV iron dose from Week 28 to Week 52, the dose of IV iron will be standardized to obtain a continuous single unit IV iron dose in terms of mg/month for the period from the Week 28 visit date to the Week 52 visit date while the subject is on treatment.
  - Note: Subjects who are randomized but never treated or who permanently discontinue study treatment on or before the Week 28 visit date will not have a value for average monthly IV iron from Week 28 to Week 52.
- IV iron therapy concomitant medication records that occur or are ongoing during the period from the subject's Week 24 visit date to the Week 52 visit date will be selected and ordered by start date and end date.
- The standardization will be carried out with the following formula:
  - Standardized IV iron dose (mg/week) = IV iron drug dose (mg) \* frequency

Note: Frequency and Gap Factors defined as follows:

Frequency (from eCRF)	Frequency (for standardization formula)	Gap Factor
-----------------------	--	------------

CONFIDENTIAL

204837

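### As worded, the evaluation-period transfusion rates include person-time from participants already off treatment at Week 28, so three exploratory descriptive rates come out too low

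*SAP*

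**What the plan says.** SAP 14.6.3.4, under the Evaluation Period entry, defines three rates per 100 patient-years: transfusion events, transfusions and units. Each numerator is restricted to treatment time; for events it is the "number of on-treatment RBC or whole blood transfusion events during the evaluation period". Under SAP 14.4.1.1 the on-treatment phase for transfusion data closes one day after the treatment stop date.

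The shared denominator adds two groups:

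- Week 28 to Week 52, "for subjects who did not withdraw from study treatment during the evaluation period";
- Week 28 to the date of stopping, "for subjects who withdrew from study treatment during the evaluation period".

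No third group covers people who had already stopped. SAP 7.4.1 sets the population for these displays: "Summary and analysis tables will use the All Randomized (ITT) population". Protocol 5.1 keeps early stoppers in follow-up ("Participants who permanently discontinue study treatment will remain in the study"), and Protocol 8.1.1 schedules their visits: "Remaining in-clinic visits: Study visits at Weeks 4, 16, 28, 40 and 52". They can therefore have real Week 28 and Week 52 dates. Where a visit is missing, SAP 14.6.1 substitutes a planned date counted from randomization.

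**The concern.** A participant who stopped at Week 20 did not stop during the EP. By elimination, the wording puts that person in the first group with the full interval. The on-treatment rule then prevents any matching event. The one exception is trivial: someone who stopped the day before Week 28 has a one-day tail. Through the planned-date rule, the same happens to randomized participants who were never treated, and to those who left or died before Week 28.

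At stake is whether each EP rate describes transfusion use per year on treatment, as its numerator implies. As written, it is a rate on treatment diluted by time off treatment. The dilution grows with early stopping, and it would differ between arms if early stopping did.

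**Working it through.** **No figure to reproduce.** The documents state no transfusion rate and no expected patient-years. The nearest planning number is in Protocol 10.1.1: up to about 10% with no hemoglobin value in the EP. That is a different quantity from the share stopping treatment before Week 28.

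**Inputs**

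- N = 268 daprodustat and 134 epoetin alfa (Protocol 10.1.1).
- EP length = 24 × 7 / 365.25 = 0.460 years.
- p = share of randomized participants off treatment before Week 28. Not given; assumed 5% to 30%.
- q = share stopping during the EP, assumed to stop at its midpoint on average. Not given; 0 and 10% tried.

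**Formulas**

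- Patient-years as written = N(1 − q) × 0.460 + Nq × 0.230
- Patient-years on treatment = N(1 − p − q) × 0.460 + Nq × 0.230
- Rate as written / on-treatment rate = on-treatment patient-years / patient-years as written = 1 − p/(1 − q/2), which is 1 − p when q = 0.

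**Results.** With q = 0, patient-years as written are 268 × 0.460 = 123.3 for daprodustat and 134 × 0.460 = 61.6 for epoetin alfa, whatever p is.

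| p | On-treatment PY, daprodustat | On-treatment PY, epoetin alfa | Rate too low, q = 0 | Rate too low, q = 10% | A true 30 per 100 PY is reported as (q = 0) |
|---|---|---|---|---|---|
| 5% | 117.1 | 58.6 | 5% | 5.3% | 28.5 |
| 10% | 110.9 | 55.5 | 10% | 10.5% | 27.0 |
| 20% | 98.6 | 49.3 | 20% | 21.1% | 24.0 |
| 30% | 86.3 | 43.1 | 30% | 31.6% | 21.0 |

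The rate of 30 is illustrative only.

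**Side-by-side reading of the arms.** Suppose the true rates are equal and q = 0. With p = 20% in one arm and 10% in the other, the reported rates stand at 0.80/0.90 = 0.89. Equal p leaves them at 1.

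**Internal check.** The Randomization to Week 52 entry of the same section cuts time at any treatment stop before Week 52. A participant who stops at Week 20 therefore contributes 20 × 7 / 365.25 = 0.383 years to the whole period, but 0.460 years to the EP, which is only part of it. The two definitions cannot both describe time on treatment.

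**Other EP endpoints.** For EP average monthly IV iron, SAP 14.6.3.2 says that participants "who permanently discontinue study treatment on or before the Week 28 visit date will not have a value". SAP 14.6.3.1 defines percent time in range only when the stop date falls after Week 28. In SAP 14.10.6, the programming note for Table 2.058 removes those who discontinued before the EP. The next two rows, Tables 2.059 and 2.060, have no such note.

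**The case against.** The best defence is that this is a drafting omission. The section counts only on-treatment transfusions, and its Day 1 to Week 52 definition truncates time at treatment stop. Saying that someone did not stop during a period can also presuppose that they were on treatment when it began. The IV iron and time-in-range exclusions are weaker precedents than they look. Both are per-participant quantities whose own denominators would generally be zero or negative for an early stopper, so they need the exclusion arithmetically; a pooled sum of person-time does not force one. All of this is fair as evidence of intent. It does not change what the formula says, and a programmer who follows it literally will produce the diluted rate.

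The second defence limits the reach, and it stands in full. A reader might infer that the treatment comparison on transfusions is biased. The documents do not support that. SAP 7.4.1 only summarizes these rates by arm, SAP 7.4 plans no testing of exploratory endpoints unless noted, and no ratio, difference or interval is defined for the EP rates. The planned between-arm transfusion analysis is the Cox model for time to first transfusion, which censors at treatment stop.

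A reader might also infer that the error flatters the arm with more treatment failure. Rescue does lead to stopping, but Protocol 8.1 also requires stopping for transplant, cancer, pregnancy and change of dialysis modality. The documents give no breakdown of early stopping by reason or arm.

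**Conclusion.** The point holds for the wording as it stands. The three EP rates per 100 patient-years in Tables 2.059 and 2.060 understate the on-treatment rate by p when nobody stops during the EP, and by slightly more otherwise. The direction is certain unless nobody is off treatment before Week 28. The size is not: the 5% to 30% range rests on an assumed p, and the q = 10% column on assumed stopping at mid-EP.

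The consequence is minor. An informal reading of the two columns would be distorted only if p differs by arm. Counts of participants transfused are also untouched, because the fault lies only in the patient-year denominator.

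**What to change.** In SAP 14.6.3.4, state that only participants on study treatment at the Week 28 date contribute EP patient-years. Their time runs from that date to the earlier of the end of the on-treatment period and the Week 52 date; everyone else contributes zero. The numerator needs no further restriction, since it is already on-treatment.

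Use one on-treatment end for both parts of the rate. SAP 14.4.1.1 ends the period one day after the stop date, while the on-treatment transfusion period in SAP 14.6.3.4 ends on the stop date, so the two must be reconciled. Add a programming note to Tables 2.059 and 2.060 to match.

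The cost is a sentence or two in the SAP and a small programming change. No new data are needed.

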**14.6.3.5. Dose Adjustment Scheme Endpoints**

Dose Adjustment Scheme Endpoints
General

• The IRT system assigns all study treatment doses in accordance with the dose adjustment scheme specified in the protocol.

• During the study, it is possible for subjects to change study treatment doses at both scheduled and unscheduled visits.

• Sites are instructed to complete an exposure record for every dose taken/planned.

CONFIDENTIAL

204837

**Dose Adjustment Scheme Endpoints****Tablet Combinations to Achieve Prescribed Daprodustat or Placebo Treatment**

Sites will enter the dose of daprodustat into exposure records. The dose steps of daprodustat are shown below:

Dosage Level  (mg)	Total Number of Tablets	Active Treatment for Daprodustat Randomized Participants						Inactive (Placebo) Treatment for Epoetin Alfa Randomized Participants	
		7 mm Placebo	2 mg Dapro	4 mg Dapro	6 mg Dapro	8 mg Dapro	10 mg Dapro	7mm Placebo	9 mm Placebo
0	1	1						1	
2	1		1					1	
4	1			1				1	
8	1					1			1
12	2				2				2
16	2					2			2
20	2						2		2
24	3					3			3
32	4					4			4
48	6					6			6

1. Dose to be administered three-times weekly

**Number of Vials and Vial Combinations to Achieve Prescribed Epoetin Alfa or Saline Treatment**

## CONFIDENTIAL

204837

Sites will enter each dose of epoetin alfa into exposure records. The dose steps of epoetin alfa (including the corresponding total weekly doses) are shown below:

Total Weekly Dose (Units)	Dose and Frequency	Epoetin Alfa Randomized Participants 					Inactive (Saline) Treatment for Daprodustat Randomized Participants
		Saline  (1 mL)	2000 U/1mL	3000 U/1mL	4000 U/1mL	10000 U/1mL	Saline  (1 mL)
0	0 U once a week	1					1
1500 	1500 U once a week		0.75				0.75
2000	2000 U once a week		1				1
3000	3000 U once a week			1			1
4000	4000 U once a week		2				2
5000	5000 U once a week		1	1			2
6000	6000 U once a week		1		1		2
8000	8000 U once a week				2		2
10,000	10,000 U once a week		1		2		3
12,000	4000 U three times a week				1		1
15,000	5000 U three times a week		1	1			2
18,000	6000 U three times a week		1		1		2
21,000	7000 U three times a week			1	1		2
24,000	8000 U three times a week				2		2
27,000	9000 U three times a week		1	1	1		3
30,000	10,000 U three times a week					1	1
36,000	12,000 U three times a week		1			1	2
42,000	14,000 U three times a week				1	1	2
48,000	16,000 U three times a week		1		1	1	3
60,000	20,000 U three times a week					2	2

1. The vial combinations used to achieve a specific weekly dose of epoetin alfa (and number of saline syringes for the corresponding inactive dose) may be adjusted by the sponsor based on changes to the commercial availability of epoetin alfa or other supply considerations. Any change to the vial combinations will be made globally across the study in order to maintain the blind, and it will be managed centrally through the IRT system. Details of any changes will be detailed in the SRM.

2. Each epoetin alfa vial should be administered using a separate syringe.

CONFIDENTIAL

204837

Dose Adjustment Scheme Endpoints

3. For saline doses, the number of 'vials' indicated in the table refers to the number of syringes containing 1 mL of saline that will be administered in order to maintain the blind.
 
4. The 1500 U epoetin alfa dose will be achieved by administering 0.75 mL of a 2000 U/mL vial. The corresponding 1500 U saline dose, for daprodustat randomized participants, will be achieved by administering 0.75 mL of saline.

Assigned Dose At A Scheduled Visit

 
The assigned dose at a particular visit refers to the dose the subject assigned based on new IRT instruction received at that visit, as recorded in the eCRF. The assigned dose at Visit X is the dose from the earliest exposure record with a start date on or after the Visit X date, but before the Visit X+1 date. 
 
For example, the assigned dose at the Week 28 visit is the dose from the earliest exposure record with a start date on or after the Week 28 visit date, but before the Week 32 visit date.
 
 
 

Most Recent Dose Prior to A Scheduled Visit / End of Treatment

 
The most recent dose prior to a particular visit refers to the dose recorded in eCRF for the subject in the period directly preceding the visit. The most recent dose prior to Visit X is the dose from the latest exposure record with a start date that is on or after the Visit X-1 date and before the Visit X date. 
 
For example, the most recent dose prior to Week 28 is the dose from the latest exposure record with a start date that is on or after the Week 24 visit date and before the Week 28 visit date.
 
 
 
If a subject permanently stops study treatment after Visit X-1 and on or before Visit X, the most recent dose prior to Visit X will be the dose from the subject's final exposure record.
 

Two Approaches to Dose Adjustment Summaries

 
The first approach counts all dose adjustments, including dose adjustments related to periods of dose holds (i.e., IRT assignment of a 0-dose).
 
The second approach does not count dose adjustments related to periods of dose holds. However, should the dose that a subject receives following a period of dose hold be different from the dose the subject received before the dose hold, this would still count as a dose adjustment in this approach.
 

Number of Dose Adjustments per Year During Day 1 - < End of Treatment

 
The number of dose adjustments per year will be determined by dividing the total number of dose adjustments between Day 1 and End of Treatment by <math>[(\text{Treatment Stop Date} - \text{Day 1 date} + 1 \text{ day}) / 365.25]</math>.
 

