7. TREATMENTS

Study treatment is defined as the investigational treatment or marketed product (i.e., daprodustat, matching placebo tablets, epoetin alfa or saline) intended to be administered to a study participant according to the study protocol.

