7.2.1.2. Daprodustat (and Placebo) Titration Doses

The available dose steps of daprodustat are outlined below (gray toned boxes indicate possible starting doses). Dose adjustments will result in the daprodustat dose being increased or decreased by one dose step at a time, as described in the dosing algorithm (Table 7). Participants who are receiving the highest dose of daprodustat (48 mg) and require an additional dose increase, will maintain the same dose. Participants who are receiving the lowest dose of daprodustat (2 mg) and require an additional dose decrease will receive placebo (0 mg) in order to maintain the blind. When a dose interruption is required by the dosing algorithm (Table 7), both daprodustat tablets and saline injections will be interrupted in order to maintain the blind.

Participants who are randomized to daprodustat treatment will also receive inactive treatment for the IV formulation (saline IV). When a dose adjustment is required for these participants, their saline IV dose will be adjusted (in addition to the daprodustat dose) in order to maintain the blind, such that the number of syringes of saline to be administered match the number of vials/syringes required for the new corresponding epoetin alfa dose (Section 7.2.2.2, Table 6).

Table 5 Tablet Combinations to Achieve Prescribed Daprodustat or Placebo Treatment

Dosage Level ¹ (mg)	Total Number of Tablets	Active Treatment for Daprodustat Randomized Participants						Inactive (Placebo) Treatment for Epoetin Alfa Randomized Participants	
		7 mm Placebo	2 mg Dapro	4 mg Dapro	6 mg Dapro	8 mg Dapro	10 mg Dapro	7mm Placebo	9 mm Placebo
0	1	1						1	
2	1		1					1	
4	1			1				1	
8	1					1			1
12	2				2				2
16	2					2			2
20	2						2		2
24	3					3			3
32	4					4			4
48	6					6			6

1. Dose to be administered three-times weekly

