
 
• The assigned dose by visit will be summarized using mean, standard deviation, minimum, P25, median, P75, and maximum by treatment group.
 
• The assigned dose by visit will also be summarized by treatment group using the number and percentage of subjects assigned to each dose level. Stacked bar graphs displaying assigned dose at all scheduled visits starting with Day 1 until Week 48 will be provided by treatment group.
 
• The median assigned dose by treatment and visit will be displayed graphically for each scheduled study visit using a line plot. The line plot of median assigned dose along with the first and the third quartiles by time will include vertical reference lines to identify the EP as well as the number of subjects by treatment group contributing to each median value.
 
• The number and percentage of patients with 0, 1, 2,....., 10 or > 10 dose adjustments will be summarized by treatment group. Summaries will be presented for the following categories of time: Day 1 – < Week 28, Week 28 – <= Week 52, and Day 1 – <= Week 52. This summary will be produced twice – the first time counting all dose adjustments, including adjustments related to periods of dose holds (i.e., no study treatment is given), the second time excluding dose adjustments related to periods of dose hold. The number and percentage of patients with dose adjustments by treatment group will also be summarized by Day 1 HemoCue Hemoglobin categories.
 
• The number of dose adjustments per subject will be summarized using mean, standard deviation, minimum, P25, median, P75, and maximum by treatment group. Summaries will be presented for the following categories of time: Day 1 – < Week 28, Week 28 – <=Week 52, and Day 1 – <= Week 52. For the period of time from Day 1 - <= Week 52, the number of dose adjustments per year will be summarized as well. This summary will be produced twice – the first time counting all dose adjustments, including adjustments related to periods of dose holds (i.e., no study treatment is given), the second time excluding dose adjustments related to periods of dose hold.
 
• The time (in days) that study treatment was withheld for HemoCue Hgb values ≥ 12 g/dL per subject will be summarized for all subjects and for subjects who had a dose hold using mean, standard deviation, minimum, P25, median, P75, and maximum by treatment group.
 

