## 14.6. Appendix 6: Derived and Transformed Data

### 14.6.1. General

Multiple Measurements at One Time Point
 
 
• Mean of the measurements will be calculated and used in any derivation of summary statistics but if listed, all data will be presented. 
 
○ Triplicate BP and HR measurements are expected at certain time points (See Section 14.2.1)
 
 
 
• Subjects having both High and Low values for Normal Ranges at any post-baseline visits for safety parameters will be counted in both the High and Low categories of “Any visit post-baseline” row of related summary tables. This will also be applicable to relevant Potential Clinical Importance summary tables.
 

Randomization Date
 
 
• Date subject was randomized
 

Treatment Start Date
 
 
• First randomized treatment dose start date
 

Last Non-Zero Dose Date
 
 
• Date of last actual dose of active study treatment from the eCRF Study Treatment/Compliance Record Form. 
 
○ The dose steps used by the dosing algorithm described in the protocol include a dose hold or a zero dose. If subjects are assigned by the algorithm to a zero dose, they only receive placebo and saline, and do not receive active study treatment for that period. When a dose interruption is required, both active treatment and placebo/saline will be interrupted. Hence, it would be possible for a subject to complete the study, while still following the dosing algorithm, but not actually taking any active study treatment. The last non-zero dose date, then captures the latest date in the study that a subject physically took a dose of active study treatment.
 
 
 

Treatment Stop Date
 
 
• Calculated as the latest study treatment dose stop date, after excluding the records for missed dose.
 

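### SAP 14.6.3.5 defines a dose hold as assignment of a 0-dose, which is a titration step, and conflicts with SAP 7.4.1, so the dose-adjustment counts that exclude holds have no single definition

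*SAP*

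**What the plan says.** **The two counts.** SAP 14.6.3.5 (Two Approaches to Dose Adjustment Summaries) describes them. On the first it says: "The first approach counts all dose adjustments, including dose adjustments related to periods of dose holds (i.e., IRT assignment of a 0-dose". On the other: "The second approach does not count dose adjustments related to periods of dose holds". There is one exception. If the dose after the hold is "different from the dose the subject received before the dose hold, this would still count as a dose adjustment in this approach".

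**The same two summaries in SAP 7.4.1.** The Dose Adjustment Scheme displays explain a hold differently: "including adjustments related to periods of dose holds (i.e., no study treatment is given".

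**What 0 means in the protocol.** Section 7.2.1.2 says that participants on the lowest daprodustat dose who "require an additional dose decrease will receive placebo (0 mg) in order to maintain the blind". Section 7.2.2.2 does the same with saline below 1500 U/week. Tables 5 and 6 list 0 as a dosage level, and note 5 to Table 7 treats the move to it as a dose decrease.

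**What an interruption is.** Under Table 7 and Sections 7.2.1.2 and 7.2.2.2, a confirmed Hgb of 12 g/dL or more stops both the active and the inactive formulation. Treatment later restarts one step lower.

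**Where the SAP separates the two.** SAP 14.6.1 (Last Non-Zero Dose Date) says: "The dose steps used by the dosing algorithm described in the protocol include a dose hold or a zero dose". It then describes each one. The exposure listing in SAP 6.2.6 has separate flags for zero dose and dose hold.

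**The concern.** The parenthesis in 14.6.3.5 gives the name of one state to another. Protocol Section 7 includes the inactive products in its definition: "Study treatment is defined as the investigational treatment or marketed product (i.e., daprodustat, matching placebo tablets, epoetin alfa or saline". A participant at 0 mg or 0 U is therefore still receiving study treatment. The explanation in 7.4.1 then covers the interruption and leaves out the 0 step, while the one in 14.6.3.5 names the 0 step. The two sections describe the same displays but select different records.

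At stake is the second count, reported in Tables 2.093 and 2.094. These tables serve the exploratory objective of evaluating the dose adjustment scheme. A step down to 0, or back up from it, is an action of that scheme. Removing it as a hold understates how often the scheme changed the dose. Leaving interruptions in would defeat the purpose of the second count.

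**Working it through.** The plan gives no figure to reproduce, so the check is to count changes under each definition.

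**Inputs**
- Daprodustat steps (protocol Table 5): 0, 2, 4, 8, 12, 16, 20, 24, 32, 48 mg.
- Restart after an interruption: one step lower (protocol Table 7).
- A net change across a hold still counts in the second approach (SAP 14.6.3.5).
- The dose sequences below are my own illustrations. H marks an interruption.

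**Rule**
- Approach 1 = number of adjacent records that differ.
- Approach 2 = the same count after deleting the records classed as holds.

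**4-2-0-2 mg (titration to 0 and back)**
- Approach 1: 4→2, 2→0, 0→2 = 3.
- Approach 2, 14.6.3.5 wording: delete 0, leaving 4-2-2 = 1.
- Approach 2, 7.4.1 wording: nothing deleted = 3.

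**4-2-0 mg (ends at 0)**
- Approach 1: 2.
- Approach 2, 14.6.3.5 wording: 4-2 = 1.
- Approach 2, 7.4.1 wording: 2.

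**12-H-8 mg (interruption, restart one step lower)**
- Approach 1: 12→H, H→8 = 2.
- Approach 2, 14.6.3.5 read literally: no 0 to delete = 2.
- Approach 2, 7.4.1 wording: 12-8 = 1.

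**12-H-8-4-2-0-2 mg (both states)**
- Approach 1: 6.
- Approach 2, 14.6.3.5 read literally: 12-H-8-4-2-2 = 4.
- Approach 2, 7.4.1 wording: 12-8-4-2-0-2 = 5.
- Approach 2, both states treated as holds: 12-8-4-2-2 = 3.

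Approach 1 does not depend on the definition. Approach 2 does in every sequence: the last one gives 3, 4 or 5, depending on the definition programmed.

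**Steps from the lowest starting doses to 0 (protocol Tables 4 to 6)**
- Daprodustat: 8→4→2→0 mg, three decreases.
- Epoetin alfa: 2000→1500→0 U, two decreases; 1500→0 U, one.

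The arms are therefore at different distances from 0, but this does not show how many participants in either arm get there.

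**The case against.** **The IRT may code an interruption as 0.** SAP 14.6.2.4 groups hold and zero-dose records as IRT-assigned when it rates compliance. If interruptions are coded as 0, the 14.6.3.5 rule would remove them as intended. A reader might infer from 14.6.3.5 alone that interruptions are certainly kept. The documents do not support that, because 7.4.1 points the other way and 14.6.2.4 leaves the coding open. The coding does not rescue the 0 step, however: 4-2-0-2 mg still falls from 3 to 1. Merging the states is harmless for compliance, where no active dose is due, but not where the dose steps themselves are counted.

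**Time held for Hgb of 12 g/dL or more.** A reader might infer that time at 0 would be counted as held time. SAP 7.4.1 and the title of Table 2.068 tie that endpoint to withholding treatment for HemoCue Hgb of 12 g/dL or more. The parenthesis in 14.6.3.5 concerns only the adjustment counts, so the endpoint is not shown to be affected.

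**Loss per participant.** It might be inferred that everyone who reaches 0 loses at least two adjustments. Someone who ends at 0 has no move out and loses one, as 4-2-0 mg shows.

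**Difference between arms.** The unequal number of steps makes a difference possible. It does not establish one, because step sizes also differ and no frequencies at 0 are given.

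**Importance.** Approach 1 is unaffected, net changes across a hold still count, and SAP 7.4 plans no testing of exploratory endpoints unless otherwise noted. This stands and limits the point to a minor correction.

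**Conclusion.** The contradiction is real. For the same two summaries, SAP 14.6.3.5 and SAP 7.4.1 define a dose hold by different records, and the protocol and SAP 14.6.1 keep those states apart. Following 14.6.3.5 as written drops genuine titrations to and from 0 in Tables 2.093 and 2.094 (1 instead of 3 for 4-2-0-2 mg). Read literally, it may also retain the interruptions that those tables are meant to exclude (2 instead of 1 for 12-hold-8 mg).

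The first result holds whichever way the IRT codes an interruption. The second rests on interruptions not being coded as 0, which the documents leave open. The counts come from assumed sequences and show direction only; the effect on the reported tables cannot be sized. No conclusion on the primary or principal secondary endpoint is touched.

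**What to change.** - Use one definition of a dose hold in SAP 7.4.1 and 14.6.3.5: an IRT interruption, identified by the dose-hold flag named in SAP 6.2.6 and not by the zero-dose flag.
- State that a move to or from 0 mg or 0 U counts as a dose adjustment in both approaches.
- State that the time-held summary uses the same dose-hold flag.

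The cost is a short SAP text change and a check that the two flags can be told apart in the exposure data. SAP 6.2.6 plans both as listing items but does not say whether they are collected or derived. No dosing rule, visit or data collection form needs to change on this account.
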